#### Daily Headache Diary

A daily headache diary will be completed for the next 12 weeks to allow for assessment of changes in headache and migraine frequency. Headache diary data will be analyzed to classify patients as “responders” (50% or greater reduction in migraine day frequency between weeks 5-8 post first erenumab treatment compared to frequency during the run-in phase) or “non-responders” (less than 50% reduction in migraine day frequency during weeks 5-8 post first erenumab treatment compared to the frequency during the run-in phase). Since patient outcome will be measured at 8 weeks (opposed to 12 weeks like is done in the majority of clinical trials), depending upon patient outcomes other definitions of “response” and “non-response” could be used. Furthermore, correlations between changes in migraine frequency and imaging outcomes could also be assessed.

A migraine day will be defined as follows: any calendar day during which a person experiences a qualified migraine headache (onset, continuation, or recurrence of the migraine headache). A qualified migraine headache is defined as a migraine with or without aura, lasting for at least 30 minutes, and meeting at least one of the following criteria (a and/or b):

- a) At least 2 of the following pain features: unilateral, throbbing, moderate to severe, exacerbated with exercise/physical activity
- b) At least 1 of the following associated symptoms: nausea and/or vomiting, photophobia and phonophobia

If the participant takes a migraine-specific medication (i.e. triptan or ergotamine) during aura or to treat headache on a calendar day, then it will be counted as a migraine day regardless of the duration and pain features/associated symptoms.

Missing values may exist in headache dairy data due to various reasons such as subjects’ missed recording, early withdrawal, or inadequate entries prohibiting evaluation of the end point (responder vs. non-responder). To impute the missing data and allow for evaluation of migraine frequency,

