(Wellcome Department of Cognitive Neurology, Institute of Neurology, London, UK) and the toolbox DPARSF interfaced with MATLAB version 11.0 (MathWorks, Natick, Ma, USA).(33) Rs-fMRI data will be pre-processed using standard procedures including the following steps: slice-time correction, motion correction, re-alignment, skull and non-brain tissue removal, spatial smoothing, and alignment to an average Montreal Neurological Institute (MNI-305) template.(34, 35) Further post-processing steps will include band-pass filtering, as well as removal of variance related to head motion, white matter signal and cerebrospinal fluid signal. Functional measurements will be imported into SPSS 21.0 (SPSS Inc, Chicago, IL) for further calculations. A region-of-interest approach will be utilized for functional connectivity analyses. The functional connectivity of 33 regions which commonly participate in pain-processing will be analyzed. Event-related BOLD data will be analyzed using a whole-brain analysis, comparing BOLD amplitude during painful stimuli vs. no stimuli. All preprocessing and general linear model (GLM) estimation of brain activation patterns for the event-related portion of the fMRI will also be performed using SPM8, interfaced with Matlab. Functional images will be realigned to the mean volume in the series, motion-corrected, realigned to each individual's structural images, normalized to standard stereotaxic space (Montreal Neurological Institute template) and smoothed using a 5 mm full width half maximum Gaussian kernel. Brain regions activated in response to painful stimuli will be identified by generating contrast maps representing brain activations associated with painful stimuli preceded by auditory cue vs. auditory cue with no painful stimuli. The BOLD signal will be modeled for each of eight successive MR frames (20 seconds) following stimulus presentation, with no assumption made about the shape of the hemodynamic response function. These contrast maps are entered into a mixed effects analysis. A main effects analysis will identify brain regions activated in subjects and a two-sample analysis will identify regions differentially activated when comparing subject cohorts. Cluster threshold correction and multiple comparisons correction will be utilized. 18 major fiber tracts will be reconstructed from DTI data using an automated technique based upon global probabilistic tractography (TRACULA).(36) This software toolbox is available online (<http://surfer.nmr.mgh.harvard.edu/>) and uses anatomical priors (T1-weighted data) as input. The robustness of the TRACULA software algorithm has been validated in prior papers.(36, 37) For each of the 18 fibertracts, tract volume, path length, axial diffusivity, radial diffusivity, mean diffusivity, and fractional anisotropy will be calculated. Arterial Spin Labeling data will be analyzed using SPM 8 and the toolbox ASLtbx.(38) SPM 8 and ASLtbx are freely downloadable online and will be interfaced with MATLAB version 11.0. ASL data will be preprocessed using standard SPM preprocessing steps including orientation resetting, image reorienting, motion correction, and co-registration (of each subjects' T1-weighted image with the ASL images) and data smoothing. Subsequent data post-processing steps will be conducted using the ASLtbx toolbox. Statistical analyses will be conducted using a GLM design.

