### Sample Size

The total sample size of 50 patients accounts for the likely scenario in which up to 15% of patients will not have full datasets due to loss-to-follow-up or unusable MRI data (e.g. patient motion, abnormal brain MRIs). Based upon the results of the phase 2 and 3 trials of erenumab and the fact that this is an open-label study, we anticipate that approximately 50% of patients will be “responders” at 8 weeks. (6-8) Thus, we would have at least 21 responders and 21 non-responders for this analysis, a sample size that is adequate for the imaging and multivariate modeling aims of this study. Sample size was determined by calculating the number of subjects needed per group to detect a difference in pain induced BOLD signal of 0.1% pre-erenumab to post-erenumab, assuming a standard deviation of 0.1. Based on a type I error of .05, a sample size of 21 patients per group will give 88% power to detect pre-treatment to post-treatment differences for responders and non-responders. The use of % signal change as the measure for calculating effect size is the standard recommendation when determining sample size for fMRI studies.(41)

Desmond and Glover, in their paper entitled “Estimating sample size in functional MRI (fMRI) neuroimaging studies: statistical power analyses”, used data from fMRI studies of cognitive function and somatosensory stimulation to estimate sample sizes needed for fMRI studies. [Desmond 2002] They concluded that for a threshold of 0.05, about 12 subjects are required to achieve 80% power at the single voxel level for typical activations. However, they state that at more realistic thresholds that approach those used after correcting for multiple comparisons, the number of subjects doubles (n=24) to maintain this level of power.

As Mumford and colleagues point out, the number of stimulations/events that are included in the fMRI paradigm must also be considered when calculating power – the more stimulations/events, the greater the power to detect a difference.(41)

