#### Analysis Plans

*Specific Aim #1 (i.e. identify changes in brain structure and function that correlate with response to erenumab):* Pre-treatment and post-treatment MRI data will be used for within and between subject

comparisons. Within subject analyses will compare baseline brain activation and perfusion patterns and functional connectivity patterns pre-treatment to post-treatment. Between subject group analyses will compare post-treatment MRI data in erenumab responders to non-responders.

Similar comparisons will be made for pre- and post-treatment pain thresholds (i.e. results of quantitative sensory testing) and cognitive testing.

So as to help with the interpretation of differences between responders and non-responders, MRI data from erenumab-treated patients will be compared to healthy non-migraine control data that we have already collected during the conduction of previous studies, when available (although we have plenty of data for the majority of analyses, we have limited ASL data and no n-back data from healthy controls). Differences in brain structure and function of migraine patients prior to erenumab treatment compared to healthy controls will be identified. Results of this analysis will determine alterations of brain structure and functions in migraine patients compared to healthy controls. Areas where migraine patients show altered structure and function will be used as regions of interest (ROIs) to assess the longitudinal, within-group changes of erenumab responders and non-responders.

Although multiple analyses are planned using functional, structural, and perfusion data, the primary analysis for specific aim #1 will be the comparison of pre-treatment pain-induced regional activation strength vs. post-treatment pain-induced regional activation strength in erenumab responders and separately in erenumab non-responders.

Post-treatment changes in other measures of brain function as well as measures of brain perfusion, brain structure, cutaneous pain thresholds and cognitive function in those responding to erenumab and in those not responding will be explored.

Two-tailed T-Tests or Mann-Whitney U tests will be used to perform group comparisons on demographic and cognitive measures and on pain threshold data. Neuroimaging data will be analyzed using general linear model designs. Within-group changes on cognitive measures, sensory testing and neuroimaging data will be assessed by applying a general linear mixed model design.

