*Specific Aim #2 (i.e. Develop models to predict which patients will respond to erenumab):* Pre-treatment scans will be used to identify MRI predictors of erenumab response. Multivariate machine-learning modeling of brain structural and functional data will be utilized for developing the predictive model. Because there are many imaging features available, but only a limited set of patients for this analysis, principal components analysis (PCA) will be performed on features collected from each imaging type to reduce the dimensionality of the data. The principal components (PCs) that result from PCA are linear combinations of the original imaging features, and can consolidate the information from the original features in such a way that only a few PCs are needed to explain most of the data variance. PCA will be performed separately on features from each imaging type to enhance clinical interpretability of PCs chosen for the predictive model.

To maximize the prediction accuracy, we will employ an ensemble learning approach by including a number of contemporary and complementary machine learning algorithms for building the predictive model, including Linear Discriminant Analysis (LDA), Quadratic Discriminant Analysis (QDA), Support Vector Machines (SVM), and Decision Tree (DT). Integrating these algorithms with Particle Swarm

Optimization (PSO)-based feature selection, we will identify the subset of features (PCs) that maximizes cross-validated accuracy of predicting responders and non-responders. Feature selection is a key step to avoid overfitting when building a predictive model with limited samples. PSO is a bio-inspired optimization algorithm that mimics the collective and collaborative behavior of social swarms in nature, e.g., colonies, honeybees, and bird flocks, in finding the optimal feature subset, and has been shown to outperform conventional feature selection algorithms in numerous recent publications.

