### **Protocol Maintenance**

Protocol modifications will be approved by the principal investigators and submitted to the Mayo Clinic IRB in accordance with Mayo IRB rules and regulations. Modifications will be documented separately and within the main protocol document with a newly assigned date and version number.

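### The responder definition behind both aims may be changed once patient outcomes are known, and nothing keeps the 50%, weeks 5-8 rule primary, requires its result to be reported, or keeps a change blind to imaging

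*Combined protocol and SAP*

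**What the plan says.** The Daily Headache Diary section of the combined protocol and SAP defines a responder as a patient with a "50% or greater reduction in migraine day frequency between weeks 5-8 post first erenumab treatment compared to frequency during the run-in phase"; a smaller reduction makes a non-responder. Because outcome is read at 8 weeks rather than the more usual 12, the section goes on to say that "depending upon patient outcomes other definitions of" response and non-response may be used. It names no alternative definition, trigger, deadline or decision-maker. It does not say whether another definition would replace the 50% rule or stand beside it. It then adds: "Furthermore, correlations between changes in migraine frequency and imaging outcomes could also be assessed".

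Three other sections depend on the label:

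- **Analysis Plans, Aim 1.** The primary analysis compares pain-induced regional activation before and after treatment "in erenumab responders and separately in erenumab non-responders". The rule is not restated there.
- **Analysis Plans, Aim 2.** Features are selected as the subset that "maximizes cross-validated accuracy of predicting responders and non-responders".
- **Sample Size.** About half the patients are expected to respond at 8 weeks, so that "we would have at least 21 responders and 21 non-responders for this analysis".

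The section on follow-up visits one to four also foresees relating the 8-week imaging to changes in migraine day frequency, without committing to that analysis. On changes to the protocol, Protocol Maintenance requires approval by the principal investigators and submission to the IRB, and says: "Modifications will be documented separately and within the main protocol document with a newly assigned date and version number".

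**The concern.** One diary-based label decides who enters each arm of the Aim 1 primary analysis and what the Aim 2 models are trained to predict. If the cut-off or the period can be changed once outcomes are in, so can the population behind each Aim 1 estimate and the target of Aim 2. A reader of the final report could not tell whether the definition used was the planned one, and the result under the planned rule might not appear.

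Timing adds to this. The last scan is at the 8-week visit, 56 days after the first treatment with a window of 3 days either way. The weeks 5-8 diary is therefore complete at about the time the last imaging is acquired. The study is open-label, and no section separates those who would choose the definition from the imaging results.

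**Working it through.** **1. The plan's own figure.** 50 × 0.85 = 42.5, hence 42 evaluable patients, or 21 and 21 at a 50% response rate. With a difference of 0.1, an SD of 0.1 and alpha 0.05 (taken as two-sided, since the Sample Size section does not say), a two-sample t-test with 21 per group has 88.5% power. This reproduces the stated 88%. That figure is not in dispute here.

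**2. Is the rule protected anywhere?**

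| Section | What it does | Keeps the 50% rule primary, requires its result, or blinds a change? |
|---|---|---|
| Daily Headache Diary | Sets the rule, then permits others | No |
| Follow-up visits | Foresees relating imaging to change in migraine days | No |
| Sample Size | Assumes about 50% response at 8 weeks | No |
| Analysis Plans, Aims 1 and 2 | Uses the label without restating the rule | No |
| Protocol Maintenance | Governs protocol modifications | Not clearly: a switch the protocol already permits need not be treated as a modification |

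**3. How many patients could change group?** The documents give no alternative cut-off and no distribution of percent reduction, so these inputs are assumed: 42 patients, percent reduction normal with mean 50 and SD 30, alternative cut-off 30%.

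Share relabelled = Φ((50 − mean)/SD) − Φ((30 − mean)/SD)

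| Mean | SD | Share | Patients of 42 |
|---|---|---|---|
| 50 | 30 | Φ(0) − Φ(−0.667) = 0.500 − 0.252 = 0.248 | 10.4 |
| 40 | 30 | Φ(0.333) − Φ(−0.333) = 0.261 | 11.0 |
| 60 | 30 | Φ(−0.333) − Φ(−1) = 0.211 | 8.9 |
| 50 | 20 | Φ(0) − Φ(−1) = 0.341 | 14.3 |
| 50 | 40 | Φ(0) − Φ(−0.5) = 0.191 | 8.0 |

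In the central case, responders go from 21 to 42 × (1 − 0.252) = 31.4 and non-responders from 21 to 10.6, or about 31/11.

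**4. Does a diary-only choice raise the type I error?** Null trials of 42 patients were simulated (40,000 per scenario), with imaging change unrelated to response and a one-sample t-test within each group. The definition was chosen from diary data alone, either as the more even of the 50% and 30% splits, or as 30% if fewer than 15 patients responded at 50%. Rejection rates were 4.7-5.1% in responders and 4.8-5.3% in non-responders, so there is no inflation.

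**5. What locking the rule could cost.** Power of a within-group test for the planned 0.1% change uses a noncentral t with n − 1 degrees of freedom and noncentrality (0.1/SD of change) × √n. The Sample Size section does not say whether its SD of 0.1 is that of the change or of a single scan. If it is per scan and the scans are uncorrelated, the SD of the change is 0.1 × √2 = 0.141. The group sizes of 12 and 8 are illustrative.

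| Patients in group | SD of change 0.1 | SD of change 0.141 |
|---|---|---|
| 21 | 99% | 87% |
| 12 | 88% | 61% |
| 8 | 68% | 41% |

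**The case against.** The plan is firmer than the open sentence alone suggests. The diary section commits to classifying patients by the 50% rule and calls responder status the end point, and the Sample Size section ties response to 8 weeks. The flexibility has a stated clinical reason, and its trigger reads as diary outcomes. All of this stands, and it limits the concern to pre-specification and reporting. It does not remove it, because a default that may be replaced depending on outcomes is not fixed.

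A reader might go further and infer that the clause inflates the type I error of the imaging tests, or that the definition would be picked to suit the imaging findings. The documents do not support that. A diary-only choice leaves the error at about 5%. Error would rise only if the definition were picked on imaging results, which the text neither proposes nor rules out. The assurance in Imaging Data Plans, "Cluster threshold correction and multiple comparisons correction will be utilized", concerns the search across the brain, not a choice between responder definitions, so it does not settle the matter either way.

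It is also fair to say that the relabelling figures rest on assumed inputs. The normal model even allows reductions above 100% (4.8% of patients in the central case), although this does not alter the relabelled share. The figures show how sensitive the label could be. They are not evidence of what will happen.

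Finally, flexibility could spare the study a very small group. That benefit is real and is counted as a cost of the fix.

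**Conclusion.** The point holds as a gap in pre-specification. The text expressly permits an outcome-dependent change to the label on which both aims rest. Nothing keeps the 50%, weeks 5-8 rule primary, obliges its result to be reported, or keeps a change blind to imaging.

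Its possible size, under the assumptions in step 3, is about 10 of 42 patients changing group (25%; 19-34% with mean 40-60 or SD 20-40, varied one at a time). The consequence is that what Aim 1 estimates and what Aim 2 predicts can be settled after outcomes are known. No claim of inflated type I error is made, and no figure is given for Aim 2 accuracy. The sentence should be corrected before response is linked to imaging. The stated 88% power is unaffected.

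**What to change.** Replace the sentence that permits other definitions with:

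> The 50% or greater reduction at weeks 5-8 v run-in is the responder definition for the Aim 1 primary analysis and the Aim 2 label, and its results will always be reported. Any other definition is exploratory, will be labelled as such, and will be fixed from diary data before imaging results by response group are seen.

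This needs no new data. The cost is that an unbalanced 50% split must be accepted: the smaller group's within-group test and the Aim 2 classifier then lose precision, for the within-group test on the scale shown in step 5.

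Optional and separate: commit to reporting the correlation of imaging change with percent reduction in migraine days as a supporting analysis. The diary and follow-up sections already foresee a correlation of this kind. Percent reduction matches the responder rule, whereas absolute change does not: 6 to 3 days is a response with a fall of 3 days (50%), while 25 to 13 is a non-response with a fall of 12 (48%). The correlation answers a different question from the within-group test and does not recover that test's power. If activation changed by the same amount in every patient whatever the response, the correlation would reject only at about its nominal 5%.

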### **Headache Characteristics (structured interview)**

How many days per month (28 days) with headache of any kind/severity: \_\_\_\_\_ / 28 days

How many days per month (28 days) with complete headache freedom: \_\_\_\_\_ / 28 days

How long do headaches last if untreated/inadequately treated: hours

How long do headaches last if successfully treated: hours

Where are they usually located (circle all that apply):

Right                    Left                    Front                    Back                    Side

Unilateral location:                    Yes                    No

Quality (circle all that apply):

Pulsating/Throbbing                    Pressure/Aching                    Stabbing                    Burning

Intensity:  
Mild                    Moderate                    Severe

Average on 0 (no pain) to 10 (most severe pain) scale: /10

Maximum on 0 (no pain) to 10 (most severe pain) scale: /10

Headaches worse with physical activity:                    Yes                    No

Headache worse with mental activity:	Yes	No
Nausea:	Yes	No
Vomiting:	Yes	No
Sensitivity to light:	Yes	No
Sensitivity to sound:	Yes	No
Conjunctival injection:	Yes	No
Tearing:	Yes	No
Nasal congestion/rhinorrhea:	Yes	No
Eyelid drooping:	Yes	No
Auras with headaches:	Yes	No
Visual:	Yes	No
Sensory:	Yes	No
Motor:	Yes	No
Dysphasia:	Yes	No
Other:	Yes	No

Percentage of headaches you experience auras: \_\_\_\_\_

When was your first headache (month and year): \_\_\_\_\_

Family history of migraine: Yes No  
 If yes, who:

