## **Headache Diary**

For what day are you recording information (month/day/year)? \_\_\_\_ / \_\_\_\_ / \_\_\_\_

What time is it right now: \_\_\_\_\_ AM PM

Did you have a headache today (circle one)? Yes No

If yes:

What day and time did the headache begin:

Date (month/day/year): \_\_\_\_ / \_\_\_\_ / \_\_\_\_

Time: \_\_\_\_\_ AM / PM (circle one)

Do you still have the headache? Yes No

If no, what time did the headache end? \_\_\_\_\_ AM / PM (circle one)

What was the peak headache severity (circle one): Mild Moderate Severe

If pain reached moderate or severe intensity, how long did it remain at that intensity?

\_\_\_\_\_ minutes or hours (circle one)

Headache Location (circle one): One side of head only Both sides of head

During the headache:

Was the headache “throbbing” in quality? Yes No

Did lights bother you more than usual? Yes No

Did sounds bother you more than usual? Yes No

Were you nauseated? Yes No

Did you vomit? Yes No

Did routine physical activity (e.g. walking, climbing stairs) make your headache worse?

How disabling was the headache/migraine (choose one):

Able to function normally

Function somewhat reduced

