### Function severely reduced

Not able to function at all (e.g. bedbound)

Did you take a medication(s) to abort this headache? Yes

No

If yes, which medication(s)?

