### Medication Name

### Number of Times Taken Today

---

---

---

---

---

---

---

---

In the past 24 hours, overall, how difficult was it to do your usual activities?

- Not difficult
- A little difficult
- Moderately difficult
- Very difficult
- Extremely difficult

In the past 24 hours how much of the time did you have difficulty moving your head?

- None of the time
- A little of the time
- Some of the time
- Most of the time
- All of the time

In the past 24 hours how much of the time did you have difficulty moving your body?

- None of the time
- A little of the time
- Some of the time
- Most of the time
- All of the time

In the past 24 hours were you able to get out of bed?

- Without any difficulty
- With a little difficulty
- With some difficulty
- With much difficulty
- Unable to do

In the past 24 hours were you able to bend over?

- Without any difficulty
- With a little difficulty
- With some difficulty
- With much difficulty
- Unable to do

In the past 24 hours were you able to do your usual activities that required physical effort?

- Without any difficulty
- With a little difficulty
- With some difficulty
- With much difficulty
- Unable to do

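### The migraine-day rule counts days with a triptan or ergotamine taken during aura, but the diary cannot identify such a day unless a headache qualifies or the drug is reported for it, so some eligibility and responder classifications may be wrong.

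*Combined protocol and SAP*

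**What the plan says.** The Daily Headache Diary section defines a migraine day by headache features. It then adds a medication clause with this condition: "If the participant takes a migraine-specific medication (i.e. triptan or ergotamine) during aura or to treat headache on a calendar day". When the condition is met, the day qualifies however short or mild the episode was. Aura and headache are alternative triggers, so the aura part can bring in days that the headache part does not.

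The diary form in the case report form appendix opens with "Did you have a headache today (circle one)? Yes No" and places the headache detail under a yes answer. Its one medication question is "Did you take a medication(s) to abort this headache". A list of drug names follows, with a column headed "Number of Times Taken Today". There is no aura item, no time of intake and no reason for intake.

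Migraine with aura is eligible (Inclusion Criteria). Triptans and ergotamine derivatives are allowed during the study (Acute Migraine Therapy).

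**The concern.** One clause of the endpoint definition has no data source. A patient who treats an aura early and gets no headache that day truthfully answers no, and nothing on the form prompts for the drug. The entry is complete. It counts towards the 80% diary compliance minimum and as an observed day, so the missing-data rules never apply to it and no query would flag it.

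The same count drives three things: the run-in check of 6-25 migraine days, the responder split on which the Aim 1 primary analysis is run, and the class that the Aim 2 models predict. Counts are small whole numbers set against hard cut-offs, so one lost day can matter for a patient near a cut-off. The loss falls only on patients who take these drugs for aura.

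**Working it through.** **1. Could another form supply the missing day?**

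- Headache Characteristics interview: asks aura type and "Percentage of headaches you experience auras". The Case Report Forms schedule places it at the first two visits only, and it is not a daily record.
- Current Medications and Other Treatments: completed by visit with dose, frequency, start and stop dates. It does not record daily intake.
- Two, Four, Eight and Twelve Week Follow-up Headache Characteristics: headache days, headache-free days and intensity. No aura or medication item.

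None fills the gap.

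**2. Which aura-treated days are lost?**

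| Same-day headache | Drug listed as aborting it | Counted? |
|---|---|---|
| Qualifying, at least 30 minutes | either | yes, on its features |
| Non-qualifying | yes | yes, as drug taken to treat headache |
| Non-qualifying | no | **no** |
| None | not asked | **no** |

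**3. Figures from the plan.** The Sample Size section gives 50 patients, up to 15% without full data and about 50% responders: 50 × 0.85 / 2 = 21.25, so 21 per group and 42 in all. A two-sided two-sample t-test with difference 0.1, SD 0.1, 21 per group and alpha 0.05 gives 88.5% power, which reproduces the stated 88%. That calculation uses no diary input, so the figure is unaffected. One wrong label is 1/42 = 2.4% of the evaluable sample.

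**4. Single patients.** Reduction = 1 − (weeks 5-8 days / run-in days); responder if at least 50%.

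- True 8 to 4: 1 − 4/8 = 50%, responder. One run-in day lost: 1 − 4/7 = 43%, recorded as non-responder.
- Recorded 8 to 4: 50%, responder. One day lost in each period means a true 9 to 5: 1 − 5/9 = 44%, non-responder.
- Recorded 10 to 5 with two run-in days and one later day lost: true 12 to 6, 50% both ways, no change.
- True run-in of 6 with one day lost: recorded as 5, which fails the lower eligibility limit.

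**5. All whole-day pairs.** Take recorded run-in from 6 to 25 and recorded weeks 5-8 from 0 up to the run-in count. That is the sum of (b + 1) for b = 6 to 25, or 330 pairs. Add the lost days back and compare labels:

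| Lost days (run-in, weeks 5-8) | Labels changed | Recorded as → full rule |
|---|---|---|
| 0, 1 | 20 (6.1%) | responder → non-responder |
| 1, 1 | 10 (3.0%) | responder → non-responder |
| 2, 2 | 20 (6.1%) | responder → non-responder |
| 1, 0 | 10 (3.0%) | non-responder → responder |
| 2, 0 | 20 (6.1%) | non-responder → responder |
| 2, 1 | 0 | none |

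These are shares of possible pairs, not probabilities.

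**6. Whole-sample size, all rates assumed.** Simulation of 400,000 patients: recorded run-in uniform on 6-25; ratio of weeks 5-8 to run-in normal with mean 0.5 and SD 0.3, clipped to 0-1.1; weeks 5-8 days binomial out of 28. About 54% are recorded responders. Lost run-in days among affected patients are Poisson. Lost days in weeks 5-8 either fall in proportion to migraine days or stay the same.

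| Affected share; mean lost days per 28 | Falling in proportion | Not falling |
|---|---|---|
| 10%; 0.5 | 0.32% (0.13 of 42) | 0.45% (0.19 of 42) |
| 30%; 1 | 1.50% (0.63 of 42) | 2.25% (0.94 of 42) |
| 50%; 2 | 3.57% (1.50 of 42) | 5.89% (2.47 of 42) |

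In the second case the recorded responder rate is too high by 0.2 to 4.2 points (53.9% against 53.7% to 49.7%). In the first it is at most 0.2 points too high.

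This simulation takes recorded run-in as already within 6-25, so it says nothing about eligibility. A figure for eligibility would rest mainly on the assumed shape near 6. With a normal run-in (mean 13, SD 5) and one such day per 28, the share of affected patients recorded below 6 is 7.6% if the distribution is clipped at 6 and 3.7% if it is truncated there. I therefore give no estimate for eligibility.

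**The case against.** The strongest reply is that the gap is narrow and largely cancels. Most routes to a migraine day stay open, as step 2 shows. The same diary serves run-in and weeks 5-8, so the omission enters both sides of the ratio, and an exactly halved loss changes no label. The Daily Headache Diary section also allows migraine frequency change to be correlated with imaging, which needs no cut-off.

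Much of this stands. A reader might infer that every aura-treated day is lost; the form does not support that, because a qualifying headache or a reported drug still makes the day count. A reader might also infer that responder labels do shift, or shift one way. The documents give neither the share of patients with aura nor the rate of aura-only treated days, and the direction depends on which period loses more.

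The reply does not remove the mismatch. Cancellation is exact only for particular pairs of losses, and the eligibility check uses run-in alone. The correlation analysis is optional and uses the same counts.

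**Conclusion.** The mismatch between rule and form is certain from the text: the aura-only clause cannot be derived from any form shown. Its effect is possible misclassification of patients with aura near the 6-day limit or the 50% cut-off; the responder label can err either way. Under the assumed ranges (10-50% of patients affected, 0.5-2 such days per 28) about 0.3-6% of labels change, or roughly 0.1-2.5 of 42. Those ranges are assumptions and not trial data, and the effect looks small under most of them. The point is still worth acting on, because a stated endpoint rule should be derivable and the correction is cheap.

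**What to change.** Add two daily diary items outside the headache questions: aura today, yes or no; and any triptan or ergotamine taken today, with or without headache, with drug name and reason. Derive the medication clause from these.

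If some patients have already completed run-in without the items, use one migraine-day rule without the aura-only clause for all patients and both periods in the primary responder label. Then apply the full rule as a sensitivity analysis in the patients who have the new items. Dropping the clause only for the earlier patients would put two migraine-day definitions into the same responder groups.

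The cost is a slightly longer daily entry and an edit to the diary form.
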